
 
Clinical assessment: To evaluate the efficacy of BDQ compared with rifamycin when administered as part of a treatment regimen with CAM and EB in adult participants with treatment-refractory MAC-LD.
 
	
 
Change from baseline in patient-reported health status on total score of SGRQ at Weeks 48 and 60.
 
Change from baseline in lung function parameters at Weeks 24, 48, and 60.
 
Percentage of participants who undergo a change in their MAC-LD treatment regimen by Week 24, by Week 48 (Group A), and by Week 60 (Group B).
 

 
Microbiological assessment: To evaluate the efficacy of BDQ compared with rifamycin when administered as part of a treatment regimen with CAM and EB in adult participants with treatment-refractory MAC-LD at Week 60.
 
	
 
Percentage of participants with sputum culture conversion (defined as 3 consecutive negative sputum cultures taken at least 25 days apart) in MGIT and 7H10 or 7H11 agar media at Week 60.
 

 
To evaluate the safety and tolerability of BDQ compared with rifamycin when administered as part of a treatment regimen with CAM and EB in adult participants with treatment-refractory MAC-LD.
 
	
 
Safety and tolerability based on assessment of AEs, clinical laboratory assessments, 12-lead ECG, vital signs, physical examination, visual examination, and audiology up to Week 60.
 

 
To evaluate the PK of BDQ (and metabolite M2), and CAM (and metabolite 4-OH-CAM [optional]).
 
	
 
PK exposures of BDQ (and metabolite M2 [optional]) at Day 1, Weeks 2, 8, 12, 24, and 48, and CAM (and metabolite 4-OH-CAM [optional]) at Day 1, Weeks 2, 8, 12, and 24.
 

Exploratory	

 
Clinical assessment: To evaluate the efficacy of BDQ compared with rifamycin when administered as part of a treatment regimen with CAM and EB in adult participants with treatment refractory MAC-LD assessed by QOL-B NTM module.
 
	
 
Change from baseline in patient reported health status on score of QOL-B NTM module at Weeks 24, 48, and 60.
 

Objectives	Endpoints

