Upon completion of the 48-week treatment period, the participants in Group A who achieved culture conversion will transfer to the follow-up period of 12 weeks. During the follow-up period, the converters will be treatment free for MAC-LD in order to confirm the durability of culture conversion. Non-converters at Week 48 in Group A will be discontinued from the study and switched to another treatment regimen if they continue chemotherapy because the duration of BDQ treatment is 48 weeks. On the other hand, the participants in Group B will continue the study intervention up to Week 60. Upon completion of the 60-week study intervention period, the study is completed, but the participant may continue SOC of local guidelines or medical practice at each study site for at least 1 year after culture conversion at the discretion of the investigators.

In addition, this study provides an option to receive BDQ-containing regimen (BDQ + CAM + EB) for non-converters in Group B at Week 24 as the optional cohort. The participants may continue Group B regimen, switch to an individualized treatment regimen, or BDQ-containing regimen in the optional cohort at the discretion of the investigators. The criteria for switching to optional cohort after Week 24 are detailed in Section 6.8.2. When the investigator changes to BDQ-containing regimen, 2-week washout of rifamycin is required before initiation of BDQ-containing regimen. The participants switching to BDQ-containing regimen will be considered treatment failures for rifamycin-containing regimen and will be followed up for efficacy and safety for BDQ-containing regimen.

In this optional cohort, during the 48-week treatment period (from Day 1 in optional cohort [OPD1] to Week 48 in optional cohort [OPW48]) of the study, participants may be changed to individualized treatment regimen. The investigators can postpone the decision to transfer to the optional cohort for up to Week 32 in order to confirm a sputum culture positive at Week 24, if necessary. Regardless of delay in the transition phase, the treatment duration of the optional cohort will be for 48 weeks.

All participants who switched to the optional cohort will be considered as treatment failure to rifamycin-containing regimen.

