The standard duration of administration with BDQ for the treatment of MDR-TB with a known bactericidal effect is 24 weeks, whereas the duration of administration with BDQ for MAC-LD, where a bacteriostatic effect is suggested, needs to be longer, and is therefore set at 48 weeks and drug free follow-up period for 3 months is planned to evaluate the recurrences after completion of treatment to evaluate appropriate treatment duration. On the other hand, the participants in Group B who achieved culture conversion at Week 24 will continue up to Week 60. This 60-week duration is consistent with the end of follow-up period in Group A. Upon completion of the 60-week study intervention period, the study is completed, but the participant may continue SOC of local guidelines in Japan, South Korea and Taiwan or medical practice at each study site for least 1 year after culture conversion at the discretion of the investigators after study completion.

In addition, participants who have not achieved culture conversion in Group A (BDQ-containing regimen) will continue their assigned regimen until Week 48, unless they have difficulty continuing due to failure to respond (see Section 6.8.1, based on non-conversion and clinical worsening) or the occurrence of AE related to the regimen. If participants were judged to have difficulty continuing due to failure to respond to the regimen or the occurrence of the regimen related AE, at the discretion of investigators, there will be options to discontinue from the study or switch to an individualized treatment regimen (in principle, add on injectable SM, injectable or inhalation suspension of AMK).

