### 6.8.2. Optional Cohort

To maximize the benefit and minimize the risk, participants in treatment Group B can switch to optional cohort after completion of Week 24 assessment. The decision to switch to optional cohort can be made by Week 32 (refer to Sections 1.2, 1.3 and 4.1). Participants must meet all of the following criteria at the timing of the decision to switch to optional cohort. Before starting BDQ administration, a washout of rifamycin for 2 weeks is required and BDQ administration in optional cohort should start by OPD1.

- Participants are non-converter based on the result of microbiological test (ie, positive) up to Week 24.
- Participants do not have condition described in Section 7.1.
- Participants do not experience any AE associated with CAM and/or EB that causes discontinuation of CAM and/or EB at the discretion of investigators.

Switching from an individualized treatment regimen to the optional cohort is not permitted.

Switching to an individualized treatment regimen is permitted if the criteria described in Section 6.8.1 are met, even after switching to the optional cohort.

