#### ***Percentage of participants who undergo a change in their MAC-LD treatment regimen***

This is to calculate the percentage of participants who have changed to an individualized treatment regimen as defined by SOC of local guidelines or protocol (Section 6.8.1) in both groups and participants who have switched to BDQ-containing regimen in Group B.

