The changes from baseline in total score of SGRQ and domain scores will be summarized descriptively at Weeks 24, 48, and 60. For the total score of SGRQ at Week 24, the difference in the change from baseline between the treatment groups will be provided using an analysis of covariance (ANCOVA) model.

- Percentage of participants who undergo a change in their MAC-LD treatment regimen.

The percentage of participants who are changed from randomized treatment regimen to the individualized treatment regimen, including switched to the optional cohort is calculated.

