
 
Clinical assessment: To evaluate the efficacy of BDQ compared with rifamycin when administered as part of a treatment regimen with CAM and EB in adult participants with treatment-refractory MAC-LD.
 
	
 
Change from baseline in patient-reported health status on total score of SGRQ at Weeks 48 and 60.
 
Change from baseline in lung function parameters at Weeks 24, 48, and 60.
 
Percentage of participants who undergo a change in their MAC-LD treatment regimen by Week 24, by Week 48 (Group A) and by Week 60 (Group B).
 

 
Microbiological assessment: To evaluate the efficacy of BDQ compared with rifamycin when administered as part of a treatment regimen with CAM and EB in adult participants with treatment-refractory MAC-LD at Week 60.
 
	
 
Percentage of participants with sputum culture conversion (defined as 3 consecutive negative sputum cultures taken at least 25 days apart) in MGIT and 7H10 or 7H11 agar media at Week 60.
 

 
To evaluate the safety and tolerability of BDQ compared with rifamycin when administered as part of a treatment regimen with CAM and EB in adult participants with treatment-refractory MAC-LD.
 
	
 
Safety and tolerability based on assessment of AEs, clinical laboratory assessments, 12-lead ECG, vital signs, physical examination, visual examination, and audiology up to Week 60.
 

 
To evaluate the PK of BDQ (and metabolite M2), and CAM (and metabolite 14-OH-CAM [optional]).
 
	
 
PK exposures of BDQ (and metabolite M2 [optional]) at Day 1, Weeks 2, 8, 12, 24, and 48, and CAM (and metabolite 14-OH-CAM [optional]) at Day 1, Weeks 2, 8, 12, and 24.
 

Exploratory	

 
Clinical assessment: To evaluate the efficacy of BDQ compared with rifamycin when administered as part of a treatment regimen with CAM and EB in adult participants with treatment refractory MAC - LD assessed by QOL-B NTM module.
 
	
 
Change from baseline in patient reported health status on score of QOL-B NTM module at Weeks 24, 48, and 60.
 

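### After Week 24 the regimen-change endpoint counts a switch that only Group B can make, so its later percentages are not comparable between arms; the by-Week-24 percentage is.

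*Protocol*

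**What the plan says.** **What is counted.** Protocol 9.4.4: "The percentage of participants who are changed from randomized treatment regimen to the individualized treatment regimen, including switched to the optional cohort is calculated". Protocol 8.1.2 gives the same rule: individualized-regimen changes "in both groups and participants who have switched to BDQ-containing regimen in Group B".

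**When.** Protocol 3 takes the percentage who "undergo a change in their MAC-LD treatment regimen by Week 24, by Week 48 (Group A), and by Week 60 (Group B"). SAP 1.1 lists the same three time points. Both documents place the endpoint under a clinical-efficacy objective comparing bedaquiline with rifamycin.

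**Who can enter the optional cohort.** Protocol 6.8.2: "participants in treatment Group B can switch to optional cohort after completion of Week 24 assessment". It adds: "The decision to switch to optional cohort can be made by Week 32"; the footnotes to the Schedule of Activities allow this to be extended. Entry requires non-conversion on cultures up to Week 24, no discontinuation condition under 7.1, and no adverse event that stops clarithromycin or ethambutol. Clinical worsening is not required.

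**Who can take an individualized regimen.** Both groups, under 6.8.1. The criterion is non-conversion together with clinical worsening, or a drug-related adverse event that makes the assigned regimen hard to continue.

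**Group A non-converters.** Protocol 4.2 says "participants who have not achieved culture conversion in Group A (BDQ-containing regimen) will continue their assigned regimen until Week 48", with an exception for failure to respond or a regimen-related adverse event. At Week 48, per 4.1, "Non-converters at Week 48 in Group A will be discontinued from the study and switched to another treatment regimen if they continue chemotherapy".

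**Analysis.** Protocol 9.4.4 says only that the percentage is calculated. SAP 5.4.1 defines no key confirmatory secondary endpoints, and SAP 5.4.2 contains neither a definition nor a method for this one.

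**The concern.** Take two participants, one per arm, both culture-positive at Week 24, clinically stable and tolerating treatment. The Group B participant may enter the optional cohort and then counts as a regimen change. The Group A participant has no equivalent route, stays on the assigned regimen and does not count. The arm, not the response, decides the score.

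Group B also accrues events for 12 more weeks. A Group A non-converter moved to other treatment at Week 48 is not counted either, mainly because that move is a study discontinuation and not an individualized regimen under 6.8.1.

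A table setting Group A at Week 48 beside Group B at Week 60, under a comparative efficacy objective, would therefore show more regimen changes on rifamycin even if the two regimens worked equally well. Readers could take access to the optional cohort for drug benefit.

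**Working it through.** **1. The plan's own figure.** Protocol 9.2: 62 per arm, 10% control conversion, a 20-point difference (so 30%), two-sided 5% chi-square, power about 80%. With mean proportion 0.20:

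z = [√62 × 0.20 − 1.960 × √(2 × 0.20 × 0.80)] / √(0.10 × 0.90 + 0.30 × 0.70) = (1.575 − 1.109) / 0.548 = 0.851, so power = 0.803.

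This reproduces. The plan gives no figure for the regimen-change endpoint.

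**2. Ceiling on the Group B-only route.** 62 × (1 − 0.10) = 55.8, about 56 participants. This is an upper limit. Analysis non-converters include deaths, discontinuations and missing samples. Entry also excludes anyone with a 7.1 condition, anyone with an adverse event stopping clarithromycin or ethambutol, and anyone already on an individualized regimen.

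**3. How few entries matter.** Assume equal efficacy and 6 of 62 individualized changes in each arm, and add 9 optional-cohort entries to Group B. Then A = 6/62 = 0.097, B = 15/62 = 0.242, pooled = 21/124 = 0.169.

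z = (0.242 − 0.097) / √(0.169 × 0.831 × 2/62) = 0.145 / 0.0674 = 2.15, so p = 0.031 (no continuity correction).

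Nine is the smallest number giving p below 0.05, and 9/56 = 16% of the ceiling. Varying the assumed individualized count:

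| Individualized changes per arm | Entries needed | Nominal p |
|---|---|---|
| 0 | 4 | 0.042 |
| 3 | 7 | 0.040 |
| 6 | 9 | 0.031 |
| 12 | 10 | 0.044 |

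**4. Splitting the two mechanisms under no drug difference.** Assumptions not in the documents: in both arms, 10% individualize by Week 24, 10% of those still at risk in Weeks 24–48, and 5% of those still at risk in Weeks 48–60. Conversion is 10% in both arms, and a share u of eligible Group B participants enters the optional cohort.

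- By Week 24: 10% in each arm, difference 0.
- Group A by Week 48: 0.10 + 0.90 × 0.10 = 19%.
- Group B eligible: 0.90 − 0.10 = 0.80.
- Group B by Week 48: 0.10 + 0.80u + (0.90 − 0.80u) × 0.10.
- Group B by Week 60: the Week 48 value plus (0.90 − 0.80u) × 0.90 × 0.05.

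| u | B by Week 48 | Excess over A | B by Week 60 | Excess over A |
|---|---|---|---|---|
| 0% | 19% | 0 | 23% | 4 |
| 25% | 37% | 18 | 40% | 21 |
| 50% | 55% | 36 | 57% | 38 |
| 75% | 73% | 54 | 74% | 55 |
| 100% | 91% | 72 | 91% | 72 |

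Excesses are in percentage points, from unrounded values. The window alone (u = 0) adds 0.81 × 0.05 = 4 points. With individualized rates of 5% or 20% in place of 10% (and half that rate in Weeks 48–60), it adds 0.9025 × 0.025 = 2 points or 0.64 × 0.10 = 6 points. The optional-cohort rule supplies the rest, and a common Week 48 cut-off by itself would leave nearly all of it.

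**5. Dropping optional-cohort entry is not clean either.** At u = 50%, individualized changes alone by Week 48 are 0.10 + 0.50 × 0.10 = 15% in Group B against 19% in Group A, because entrants leave the set at risk of an individualized change. The bias reverses.

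**The case against.** A reader might infer that the whole endpoint favours bedaquiline by construction. The documents do not support that. The first time point is by Week 24, with one window for both arms, and optional-cohort entry cannot precede the Week 24 assessment, so neither mechanism touches it.

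A reader might also infer that a biased comparison will be claimed as evidence of efficacy. No test, contrast or model is specified here, unlike conversion, negativity, time to conversion and SGRQ, and the SAP treats secondaries as supportive. Optional-cohort data are to be analysed separately (Protocol 9.4.1). SAP 5.2 counts optional-cohort and individualized switches on separate lines, and SAP 5.6.1 summarizes individualized switches alone.

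Nor is it true that Group A non-converters cannot be counted: 4.2 lets them change regimen for failure to respond or an adverse event. The unequal windows are labelled by group and follow the planned treatment durations. Counting entry as a change fits the protocol's rule that such participants are rifamycin treatment failures.

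All of this stands, and it limits the point to descriptive reading after Week 24. It does not remove it. The composite in Protocol 8.1.2 and 9.4.4 still governs a comparative efficacy endpoint, nothing in SAP 5.4.2 redefines it, and separate disposition counts do not change what the endpoint measures.

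**Conclusion.** The point holds for the Week 48 (Group A) and Week 60 (Group B) percentages and not for the by-Week-24 percentage. The later reads differ by arm even with equal efficacy, chiefly because of the optional-cohort rule; the 12-week window is minor, about 4 points (2 to 6) under the stated assumptions.

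The size depends on uptake, which the documents do not give. Up to about 56 of 62 Group B participants, a ceiling, could be counted through a route closed to Group A. Entry by 9 would suffice for nominal p = 0.031 if each arm had 6 individualized changes. That p-value is only a yardstick for how visible the artefact would be, since no test is planned. The primary endpoint and its conclusion are unaffected.

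**What to change.** Amend Protocol 3, 8.1.2 and 9.4.4 and SAP 1.1, and add the missing definition and method to SAP 5.4.2:

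- Make the by-Week-24 percentage the only between-group comparison for this endpoint.
- After Week 24, tabulate individualized-regimen changes and optional-cohort entry as separate components, to a common Week 48 cut-off in both arms, with optional-cohort entry as a competing event for individualized change.
- Report individualized switches made after optional-cohort entry (6.8.2 permits them) within the optional cohort.
- Report Week 48–60 changes for Group B only, outside the comparison.

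This changes definitions and tables only, not treatment rules, visits or data collection. SAP 5.2 already requires the two switch counts. The cost is slightly more tabulation and a late contrast that looks less favourable to bedaquiline.

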#### **9.4.5. Tertiary/Exploratory Endpoint**

The changes from baseline in score of QOL-B NTM module and domain scores will be summarized descriptively at Weeks 24, 48, and 60.

For participants who achieved sputum culture conversion, the changes from baseline in the total score of SGRQ, the score of QOL-B NTM module, and chest CT findings will be evaluated.

The relationship between BDQ and CAM PK and MAC-LD treatment outcome and safety endpoints will be evaluated. PK/PD analyses will be performed on the collected data when all participants have reached Week 24 or discontinued earlier. The PK/PD analyses may be performed at earlier time points as necessary to support efficacy and safety findings. If there is any visual trend in graphical analysis, suitable models will be applied to describe the PK/PD relationships. The results of the PK/PD evaluations will be presented in a separate report. Other exploratory endpoints specified in Section 3, [OBJECTIVES AND ENDPOINTS](#) will be analyzed descriptively.

#### **9.4.6. Safety Analyses**

All safety analyses will be made on the Safety Population.

#### **Adverse Events**

The verbatim terms used in the eCRF by investigators to identify AEs will be coded using the Medical Dictionary for Regulatory Activities (MedDRA). Treatment-emergent AEs are AEs with onset during the treatment period or that are a consequence of a preexisting condition that has worsened since baseline. All reported treatment-emergent AEs will be included in the analysis. For each AE, the percentage of participants who experience at least 1 occurrence of the given event will be summarized by treatment group. In addition, comparisons between treatment groups will be provided if appropriate.

Summaries, listings, datasets, or participant narratives may be provided, as appropriate, for those participants who die, who discontinue study intervention due to an AE, or who experience a severe AE of at least Grade 3 or an SAE.

### **Clinical Laboratory Tests**

Laboratory data will be summarized by type of laboratory test. Reference ranges and markedly abnormal results (specified in the SAP) will be used in the summary of laboratory data. Descriptive statistics will be calculated for each laboratory analyte at baseline and for observed values and changes from baseline at each scheduled time point. Changes from baseline results will be presented in pre- versus postintervention cross-tabulations (with classes for below, within, and above normal ranges). Frequency tabulations of the laboratory abnormalities will be made. A listing of participants with any laboratory results outside the reference ranges will be provided. A listing of participants with any markedly abnormal laboratory results based on DMID scale (defined in SAP) will also be provided.

### **Electrocardiogram**

The effects on cardiovascular variables will be evaluated by means of descriptive statistics and frequency tabulations. These tables will include observed values and changes from baseline values (the predose ECG will be used as baseline).

Electrocardiogram data will be summarized by ECG parameter. Descriptive statistics will be calculated at baseline and for observed values and changes from baseline at each scheduled time point. Frequency tabulations of the abnormalities will be made.

The ECG variables that will be analyzed are heart rate, PR interval, QRS interval, QT interval, and QTc interval using some of the following correction methods: QT corrected according to Bazett's formula (QTcB), QTcF.

Descriptive statistics of QTc intervals and changes from baseline will be summarized at each scheduled time point. The percentage of participants with QTc interval >450 milliseconds (ms), >480 ms, or >500 ms will be summarized, as will the percentage of participants with QTc interval increases from baseline >30 ms or >60 ms.

All clinically relevant abnormalities in ECG waveform that are changes from the baseline readings will be reported (eg, changes in T-wave morphology or the occurrence of U-waves).

### **Vital Signs**

Vital signs including temperature (axillary), heart rate, respiratory rate, oxygen saturation, and blood pressure (systolic and diastolic) (supine or sedentary after at least 5 minutes rest) values and changes from baseline will be summarized at each scheduled time point. The percentage of participants with values beyond clinically important limits based on DMID scale (defined in SAP) will be summarized.

**Physical Examination, Visual Examination, and Audiology**

Descriptive statistics of changes from baseline will be summarized at each scheduled time point.

Physical examination findings will be summarized at each scheduled time point. Descriptive statistics will be calculated at baseline and for observed values and changes from baseline at each scheduled time point. Frequency tabulations of the abnormalities will be made. Visual acuity, color discrimination, visual field, fundoscopy, and audiometry data will be descriptively presented.

